	≥ 160 mm Hg (systolic) OR ≥ 110 mm Hg (diastolic)	
 Reduce cabozantinib by one dose level or interrupt cabozantinib treatment per investigator discretion Add new or additional anti-hypertensive medications and/or increase dose of existing medications and monitor subject closely for hypotension. If optimized antihypertensive therapy (usually to include 3 agents) does not result in BP < 150 mm Hg systolic or < 100 mm Hg diastolic, cabozantinib treatment should be dose reduced further or interrupted Cabozantinib treatment should be dose interrupted if upper limits of systolic BP (≥ 160 mm Hg) are sustained and not adequately manageable or if systolic BP is > 180 mm Hg or diastolic BP > 110 mm Hg, or if subject is symptomatic Re-start cabozantinib treatment at the most tolerable dose and re-escalate only if BP falls to and is sustained at < 150 mm Hg systolic and < 100 mm Hg diastolic
	Hypertensive emergency	
 Discontinue cabozantinib treatment
Hand-Foot Syndrome	Grade 1	
 Cabozantinib treatment may be continued at the current dose if PPES is clinically insignificant and tolerable. Otherwise, cabozantinib should be reduced to the next lower dose level. Start urea 20% cream twice daily AND clobetasol 0.05% cream once daily. Reassess at least weekly; if PPES worsens at any time or does not improve after 2 weeks, proceed to the intervention guidelines for Grade 2.

	Grade 2	
 • Cabozantinib treatment may be continued if PPES is tolerated. Cabozantinib should be dose reduced or interrupted if PPES is intolerable. Continue urea 20% cream twice daily AND high potency steroid cream (e.g., clobetasol 0.05%) once daily and add analgesics (e.g., NSAIDs/gamma-aminobutyric acid agonists) for pain control if needed. Reassess at least weekly; if PPES worsens or affects self-care, proceed to the intervention guidelines for Grade 3.
	Grade 3	
 • Interrupt cabozantinib treatment until severity decreases to Grade 1 or 0. Continue treatment of skin reaction with high potency steroid cream (e.g., clobetasol 0.05%) twice daily AND analgesics. Resume study drug at a reduced dose if PPES recovers to Grade \leq 1. Discontinue subject from study treatment if PPES does not improve within 6 weeks.

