Proteinuria	\leq 1 mg/mg (\leq 113.1 mg/mmol)	
 • No change in cabozantinib treatment or monitoring
	> 1 and < 3.5 mg/mg (> 113.1 and < 395.9 mg/mmol)	
 • Consider confirming with a 24-h protein assessment within 7 days • No change in cabozantinib treatment required if UPCR \leq 2 mg/mg or urine protein \leq 2 g/24 h on 24-h urine collection. • Dose reduce or interrupt cabozantinib treatment if UPCR > 2 mg/mg on repeat UPCR testing or urine protein > 2 g/24 h on 24-h urine collection. Continue cabozantinib on a reduced dose if UPCR decreases to < 2 mg/mg. Consider interrupting cabozantinib treatment if UPCR remains > 2 mg/mg despite a dose reduction until UPCR decreases to < 2 mg/mg. Restart cabozantinib treatment at a reduced dose after a dose interruption. • Repeat UPCR within 7 days and once per week. If UPCR < 1 mg/mg on 2 consecutive readings, UPCR monitoring can revert to protocol-specific times. (Second reading is confirmatory and can be done within 1 week of first reading.) If UPCR remains > 1 mg/mg and < 2 mg/mg for 1 month or is determined to be stable (< 20% change) for 1 month, check urine protein/creatinine per protocol or as clinically indicated.
	Nephrotic syndrome	
 • Discontinue cabozantinib treatment
Osteonecrosis (including jaw)	Grade 1-4	
 • Discontinue cabozantinib treatment

Other toxicity possibly attributable to study treatment	Intolerable Grade 2 that cannot be adequately managed	
 • Hold treatment or dose reduction at discretion of treating investigator. • Note: It is recommended that dose holds be as brief as possible.
	Grade 3	
 • Hold treatment and monitor toxicity every 1-2 weeks. If toxicity resolves to \leq Grade 1 (or baseline) within 6 weeks, treatment may be resumed with one dose level reduction. • Note: It is recommended that dose holds be as brief as possible.
	Grade 4	
 • Discontinue cabozantinib unless the following criteria are met: 
 ○ Subject is deriving clear clinical benefit as determined by the investigator ○ Toxicity can be managed with a dose reduction following recovery to Grade 1 (or baseline) and optimal medical care

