9.1.9 Adverse Effects

1. Adverse Effects: Adverse reactions occurring in $\geq 20\%$ of cabozantinib-treated patients in the CELESTIAL clinical trial in patients with HCC, in order of decreasing frequency were: diarrhea, decreased appetite, palmar-plantar erythrodysesthesia (PPES), fatigue, nausea, hypertension, and vomiting (Abou-Alfa, Meyer et al. 2018). Grade 3-4 adverse reactions which occurred in $\geq 5\%$ of patients were PPES, hypertension, fatigue, diarrhea, asthenia, and decreased appetite. There were 6 adverse reactions leading to death in patients receiving cabozantinib (hepatic failure, hepatorenal syndrome, esophagobronchial fistula, portal vein thrombosis, pulmonary embolism,

upper gastrointestinal hemorrhage). Other described AEs include GI fistulas and perforation (1%), thrombotic events (7%), jaw osteonecrosis (<1%), wound complications in the perioperative period, and Reversible Posterior Leukoencephalopathy Syndrome.

For a full description of the safety profile of cabozantinib across multiple cancers, refer to the Cabozantinib Investigator's Brochure.

Adverse events may occur within the first few weeks in the course of treatment with cabozantinib, as cabozantinib is expected to reach steady state exposure at approximately 2 weeks following first dose. Events that generally have an early onset include hypocalcemia, hypokalemia, thrombocytopenia, hypertension, PPES, abdominal pain, mucosal inflammation, constipation, diarrhea, and vomiting.

2. Pregnancy and Lactation: Category D. Based on animal data cabozantinib can cause fetal harm when administered to a pregnant woman.
3. Drug Interactions:
 - Strong CYP3A4 Inhibitors:** Coadministration of a cabozantinib capsule formulation with a strong CYP3A4 inhibitor increased the exposure of cabozantinib, which may increase the risk of exposure-related adverse reactions. Avoid coadministration of cabozantinib with strong CYP3A4 inhibitors. Reduce the dosage of cabozantinib if coadministration with strong CYP3A4 inhibitors. Reduce the dosage of CABOMETYX if coadministration with strong CYP3A4 inhibitors cannot be avoided. Avoidance of grapefruit or grapefruit juice is recommended due to the potential for increased exposure of cabozantinib.

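### Table 4 needs reconciling in two places: discordant proteinuria tests trigger both of two dose instructions, and tolerable but clinically significant hand-foot syndrome is handled more strictly at grade 1 than at grade 2

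*Combined protocol and SAP*

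**What the plan says.** Section 5.2, Table 4 sets the cabozantinib action for each non-hematologic toxicity.

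Hand-foot syndrome (PPES):
- Grade 1: the drug "may be continued at the current dose if PPES is clinically insignificant and tolerable. Otherwise, cabozantinib should be reduced to the next lower dose level".
- Grade 2: "Cabozantinib treatment may be continued if PPES is tolerated. Cabozantinib should be dose reduced or interrupted if PPES is intolerable".
- The grade 1 row also routes patients onward: "if PPES worsens at any time or does not improve after 2 weeks, proceed to the intervention guidelines for Grade 2".

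Proteinuria, row for UPCR above 1 and below 3.5 mg/mg:
- A second test is optional: "Consider confirming with a 24-h protein assessment within 7 days".
- First action bullet: "No change in cabozantinib treatment required if UPCR \leq 2 mg/mg or urine protein \leq 2 g/24 h on 24-h urine collection".
- Second action bullet: "Dose reduce or interrupt cabozantinib treatment if UPCR > 2 mg/mg on repeat UPCR testing or urine protein > 2 g/24 h".

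Two other places matter. Sections 5.1.2 and 5.2 say that a dose modification which the treating investigator judges necessary for safety during the DLT window is itself a DLT, even if no explicit criterion is met. Section 5.2 also says that modifications are not permitted in that window. The explicit criterion for non-hematological toxicity in Section 5.1.2 starts at grade 3. Section 9.1.9 places PPES among the early effects of the drug: "Events that generally have an early onset include hypocalcemia, hypokalemia, thrombocytopenia, hypertension, PPES".

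**The concern.** A dose-modification table should give one action for one set of findings, and the action should not become lighter as the grade rises unless the table explains why. Neither property holds throughout Table 4.

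In the proteinuria row, a site holding two discordant results can follow either bullet and be within the protocol. In the PPES rows, the condition for continuing is tighter at grade 1 than at grade 2.

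The PPES point reaches the primary endpoint. DLT status during the first 29 days drives the TITE-CRM, which assigns doses and selects the MTD/RP2D from 32 patients against a 35% threshold. If a milder reaction can be scored as a DLT and a more severe one not, the toxicity input to the model is not ordered by severity for those patients.

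**Working it through.** There is no planned figure to reproduce. The check is to write out each rule and list every combination.

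**Step 1, PPES.** Inputs are the grade 1 and grade 2 rows of Table 4. Grade 1 continues only if the reaction is both clinically insignificant and tolerable. Grade 2 depends on tolerability alone.

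| Reaction | Grade 1 row | Grade 2 row |
|---|---|---|
| insignificant, tolerable | may continue, current dose | may continue |
| significant, tolerable | should be reduced | may continue |
| insignificant, intolerable | should be reduced | reduce or interrupt |
| significant, intolerable | should be reduced | reduce or interrupt |

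All eight cells give exactly one instruction. The severity order is reversed in one line only, the tolerable but clinically significant reaction. The protocol does not define clinical insignificance, so the boundary of that line is left to judgement.

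**Step 2, from PPES to the DLT.** Take that line within the first 29 days.
- Grade 1: no explicit DLT criterion is met, since grade 3 is needed. Table 4 says to reduce. If the investigator judges the reduction necessary for safety, it is a DLT.
- Grade 2, tolerated and continued: no explicit criterion is met and nothing is modified, so it is not a DLT.

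**Step 3, proteinuria.** Let A be UPCR at or below 2 mg/mg and B be 24-hour protein at or below 2 g. The no-change bullet applies if A or B holds. The reduce-or-interrupt bullet applies if the repeat UPCR is above 2 or the 24-hour protein is above 2 g. With both a repeat UPCR and a 24-hour result in hand, both bullets apply when exactly one of A and B is true.

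| Repeat UPCR (mg/mg) | no 24-h test | 24-h 1.5 g | 24-h 2.0 g | 24-h 2.5 g |
|---|---|---|---|---|
| 1.5 | no change | no change | no change | both |
| 2.0 | no change | no change | no change | both |
| 2.5 | reduce/interrupt | both | both | reduce/interrupt |

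Four of these 12 illustrative combinations trigger both bullets. That count shows where the conflict lies; it is not a frequency among patients. Concordant results, or UPCR alone, give one answer.

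**Step 4, from proteinuria to the DLT.** Table 5 schedules routine UPCR only on Day 1 of each cycle, so the first scheduled value after the start of treatment is Cycle 2 Day 1, which is day 29. The weekly repeats in Table 4 begin only after a value above 1 mg/mg. The route from this conflict to DLT status is therefore weak.

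**The case against.** The PPES rows cover different grades, each patient falls in one row, and each cell gives one instruction. The grade 2 wording is permissive and does not say that the dose stays unchanged, so an investigator may still reduce. This stands: the PPES finding is an inverted ordering, not a self-contradiction. A reader might infer that like patients receive opposite dose actions, but the grades differ, and *should reduce* against *may continue* is not a pair of opposites.

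A reader might also infer that the two-week routing rewards persistence, because an unimproved grade 1 reaction moves to the more permissive row. The documents do not carry that far. A clinically significant grade 1 patient should already have been reduced, continuing does not restore the earlier dose, and re-escalation is handled separately in Section 5.2.1.

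The DLT consequence is not automatic. It needs the one reversed line, an onset within 29 days and the investigator's judgement that the change is necessary for safety. That also stands, and it is why the point is that severity *can* be reversed in the endpoint, not that it will be.

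For proteinuria, the 24-hour test is optional, saying that no change is required does not forbid a change, and the reduce bullet refers to a repeat UPCR. With an initial UPCR above 2, a 24-hour result at or below 2 g and no repeat yet, only the no-change bullet applies. It would therefore be wrong to say that any disagreement triggers both. What remains is that, once a repeat UPCR and a 24-hour result fall on opposite sides of 2, both bullets apply and nothing ranks the tests. A confirmatory test matters most when it disagrees.

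**Conclusion.** The point holds in a limited form. The proteinuria row gives one patient two conflicting instructions when the optional 24-hour result and the repeat UPCR disagree about 2. The PPES rows reverse the severity order for tolerable but clinically significant reactions, and through the dose-modification clause that reversal can reach the primary endpoint.

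No magnitude can be stated. Two estimates are tempting and neither is supported:
- Assuming that 10-20% of patients have tolerated grade 1-2 PPES by day 29 gives 0.10 × 32 = 3.2 to 0.20 × 32 = 6.4 patients. Most of the categories counted there have no change of action: tolerated grade 2 and insignificant, tolerable grade 1 may both continue. Only tolerable, clinically significant grade 1 reactions matter, and Section 9.1.9 gives no rate for them.
- Since 24-hour protein equals UPCR times 24-hour creatinine *c* in grams, the 24-hour threshold is crossed at UPCR = 2/*c*. With assumed *c* of 0.7, 1.0 and 1.4 g/day, the crossing is at 2.86, 2.00 and 1.43. The discordant width is then 0.86, 0 and 0.57 out of a row range of 2.5, or 34%, 0% and 23%. These are shares of an interval, not of patients, and they include zero.

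This is a minor finding, but it is more than missing detail, because it changes the dose action and possibly DLT status.

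**What to change.** The sponsor's clinical team should reconcile the grade 1 and grade 2 PPES rows with each other and with the DLT rule in Sections 5.1.2 and 5.2. It should also reconcile the two proteinuria bullets so that exactly one instruction applies to any pair of UPCR and 24-hour results. The clinical content of both rules is for that team to decide.

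Cycle-1 PPES dose reductions should be listed by grade, so that the DLT status of each can be checked.

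The cost is table wording in the next amendment and one listing. No new assessments are needed.

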5.3 Concomitant Medications/Treatments

The following concomitant medications or treatments are not permitted while the patient is currently receiving therapy on the protocol:

- Other investigational agents or anticancer treatment
- Concurrent radiation or other locoregional therapy
- Strong CYP3A4 inhibitors and inducers (see Appendix III)
- Oral anticoagulants (e.g., warfarin or other coumarin-related agents, direct thrombin or direct FXa inhibitors, or antiplatelet agents such as clopidogrel, or chronic use of aspirin above low dose levels for cardioprotection per local applicable guidelines).
- Erythropoietic stimulating agents (e.g., epoetin alfa and darbepoetin alfa)

The following concomitant medications or treatments are to be used with caution while the patient is currently receiving therapy on the protocol:

- Drugs that prolong the QTc interval should be avoided if possible, as cabozantinib can prolong the QTc interval
- Drugs known to be P-glycoprotein substrates (e.g. fexofenadine, aliskiren, ambrisentan, digoxin, colchicine, maraviroc, posaconazole, tolvaptan, etc.) should be used with caution as cabozantinib can cause increased P-glycoprotein substrate plasma concentrations.
- MRP2 inhibitors such as cyclosporine, delavirine, efavirenz, and emtricitabine should be used with caution during treatment with cabozantinib as coadministration can cause increased cabozantinib plasma concentrations.
- Highly protein-bound medications (e.g. diazepam, furosemide, dicloxacillin, propranolol, etc.) should be used with caution during treatment with cabozantinib.
- Grapefruit, star fruit, and seville oranges may also increase plasma concentrations of cabozantinib and should be avoided.

5.4 Other Modalities or Procedures

None

5.5 Duration of Therapy

Treatment may continue for a total of 2 years or until one of the following criteria apply:

- Disease progression as defined in Section 7.0
- Inter-current illness that prevents further administration of treatment
- Unacceptable adverse event(s)
- Sexually active subjects who refuse to use medically accepted barrier methods of contraception (e.g., male condom, female condom) during the course of the study and for 4 months after discontinuation of study treatment
- Patient who becomes pregnant or is breastfeeding
- Patient who cannot tolerate the minimum protocol-specified dose of study treatment
- Request by regulatory agencies for termination of treatment of an individual subject or all subjects under the protocol
- Significant noncompliance with the protocol schedule in the opinion of the investigator
- Patient voluntarily withdraws from treatment **OR**
- General or specific changes in the patient's condition render the patient unacceptable for further treatment in the judgment of the investigator

5.6 Off Treatment Criteria

Patients will be removed from protocol therapy when any of the criteria listed in Section 5.5 apply. Document in the source the reason for ending protocol therapy and the date the patient was removed from treatment. All patients who discontinue treatment should comply with protocol specific follow-up procedures as outlined in Section 5.7. The only exception to this requirement is when a subject withdraws consent for all study procedures or loses the ability to consent freely.

5.7 Duration of Follow-Up

After treatment discontinuation, follow-up for survival and initiation of any other anti-cancer therapies will be documented every 3 months (+/- 1 week) via telephone or office visit documentation for up to 2 years from treatment discontinuation or until death, whichever comes first, or 3 years after first date of treatment initiation for those that remain on treatment. Patients removed from treatment for unacceptable adverse events will also be followed more closely until resolution or stabilization of the adverse event.

5.8 Off Study Criteria

Patients can be taken off study at any time at their own request, or they may be withdrawn at the discretion of the investigator for safety, behavioral or administrative reasons. The reason(s) for discontinuation from study will be documented and may include:

- 5.8.1** Patient withdraws consent (termination of treatment and follow-up);
- 5.8.2** Loss of ability to freely provide consent through imprisonment or involuntary incarceration for treatment;
- 5.8.3** Termination of the study by the Sponsor, the University of Michigan, or the FDA;
- 5.8.4** Patient completes protocol treatment and follow-up criteria;

5.9 Patient Replacement

All patients who receive at least one dose of study therapy will be considered evaluable for primary endpoint and safety/toxicity.

Patients enrolled in the study will be considered non-evaluable for efficacy under the following case scenarios and replaced by additional patients:

1. Patients who received no investigational therapy.
2. Patients meeting off study criteria 5.8.1 and 5.8.2. As this trial assigns the dose level based upon real-time assessment of the experience of those treated on trial, any partial data from a patient stopping trial therapy early while still within the observation period for dose-limiting toxicity due to criteria 5.8.1 and 5.8.2, will continue to have their partial data used for dose assignments for future patients. However, this type of patient, stopping treatment due to 5.8.1 and 5.8.2 would be replaced to reach the trial's total sample size.

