11.2 Sample Size and Accrual

[figure not shown]
The study will enroll 32 patients for the estimates of the dose-toxicity function. Patients will be recruited as available and assigned to treatment according to the estimate probability of DLT as described above. No formal cohort size is required; however, at least two patients must be observed for their entire acute toxicity period (29 days) before dose escalation is allowed.

The operating characteristics of this trial design were evaluated through simulation, both near to and far from our expectations for toxicity. Table 7 lists our prior expectations for toxicity at each dose level and the simulated 'truth' for the four simulation scenarios. The simulation scenarios are: 1 – our prior expectations for toxicity are correct, 2 – our prior expectations moderately underestimate the true probability of toxicity at all dose levels, 3 – our prior expectations moderately overestimate the true probability of toxicity at all dose levels, and finally 4 – our prior expectation severely underestimated the true probability for toxicity. The MTD or RP2D is in gray; the dose level with the highest estimated probability of dose-limiting toxicity not exceeding 0.35.

Table 7. Operating Characteristics for Trial Schema					
Dose Level	Expectation for probability of DLT	Scenario 1	Scenario 2	Scenario 3	Scenario 4
0	20%	20%	20%	15%	45%
1*	27%	27%	35%	20%	60%
2	35%	35%	50%	30%	75%
Other Variables		Scenario 1	Scenario 2	Scenario 3	
Probability of early termination (PET)		17%	32%	7%	
Expected number (EN) of patients treated at MTD		16	12	22	
Probability of selecting correct dose level as MTD		70%	40%	90%	

**starting dose level*

The following figure displays the operating characteristics for this trial design under the four scenarios. The simulations indicate that this design does a good job of choosing the MTD or RP2D and treats a majority of patient at that dose level under scenarios both near to and far from expectations. The trial also stops early and protects the patient from the possibility of unjustifiable probability of DLT when the reality of the probability of DLT is moderately to severely higher than what we expect.

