11.4 Data Analyses Plans

The TiTE-CRM estimates for the probability of DLT will be reported with 95% Bayesian Credible intervals, once the 32nd evaluable patient has completed the DLT observation period. The MTD/RP2D will be determined at that time as the dose level with the highest probability of DLT not exceeding 35%.

We will record ORR as a yes/no outcome for each patient for the period of active study treatment and report the estimate and exact 95% binomial confidence intervals. We will estimate PFS and OS using the product-limit method of Kaplan and Meier. Follow-up time will be defined as time from date of first study treatment until the date of radiological or clinical progression (leading to withdrawal from the study), or death from any cause, whichever comes first for PFS and for only death from any cause for OS. For patients without events, we will censor the follow-up time at the date of last disease evaluation at the time of analysis. We will report estimates for the median and 75th percentiles with 95% confidence intervals. We will summarize additional safety data (e.g., laboratory safety parameters, vital signs, concomitant medications and new physical examination findings) descriptively by reporting counts and percentages, with exact binomial confidence intervals where appropriate. ORR will be determined as per the RECISTv1.1 guidelines. We will report adverse events per the NCI CTCAE v5.0.

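### Section 5.9 excludes treated patients from efficacy if they withdraw consent at any time, contrary to 7.1.1 and 11.4, and leaves the 32nd evaluable patient undefined

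*Combined protocol and SAP*

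**What the plan says.** Section 5.9 opens with a broad rule for the primary endpoint: "All patients who receive at least one dose of study therapy will be considered evaluable for primary endpoint and safety/toxicity". It then turns to efficacy: "Patients enrolled in the study will be considered non-evaluable for efficacy under the following case scenarios and replaced by additional patients". The first case is patients who never received study drug. The second is "Patients meeting off study criteria 5.8.1 and 5.8.2".

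Criterion 5.8.1 reads "Patient withdraws consent (termination of treatment and follow-up"; 5.8.2 is loss of the ability to consent freely. Section 5.8 sets no time limit: "Patients can be taken off study at any time at their own request". Under 5.7, survival follow-up runs for up to 2 years after treatment ends.

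The rest of the second case in 5.9 concerns "any partial data from a patient stopping trial therapy early while still within the observation period for dose-limiting toxicity". Those partial data stay in use for dose assignment, and this type of patient is replaced so that the total sample size is reached.

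Three other places bear on the point:

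- Section 7.1.1 counts as evaluable for response anyone with at least one cycle and a disease re-evaluation (or objective progression before the end of cycle 1). It makes every dosed patient evaluable for DLT, and names only never-treated patients for replacement.
- Section 11.4 records ORR for each patient. It estimates PFS and OS by Kaplan-Meier, censoring patients without events at the last disease evaluation. It reports the final TITE-CRM estimates "once the 32nd evaluable patient has completed the DLT observation period".
- Section 11.2 gives the total: "The study will enroll 32 patients for the estimates of the dose-toxicity function".

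**The concern.** Whether a treated patient belongs to the efficacy set under 5.9 depends on something that happens after treatment starts. Patients who live longer have more time in which to withdraw; patients who have just progressed may have more reason to. Excluding them selects the set on an event related to outcome, and the direction of the resulting bias cannot be known in advance. PFS, TTP and OS do not need the exclusion, because censoring already handles incomplete follow-up.

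The sections also disagree. With 5.9 on one side and 7.1.1 and 11.4 on the other, the efficacy set of a small single-arm trial could be chosen after outcomes are known.

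The second issue is the count. A dosed patient who withdraws is evaluable for the primary endpoint but is replaced to reach the total. It is therefore unclear which patient is the 32nd evaluable one, and when the RP2D is fixed. A patient who leaves inside the window is evaluable by definition yet can never complete it.

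**Working it through.** **The plan's own figure.** The 32 in 11.2 rests on TITE-CRM simulations. The documents do not give the dose-toxicity model, prior variance, accrual rate or numerical stopping rule, so 32 cannot be re-derived. The points below do not depend on it.

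**1. Which efficacy set?** Take a treated patient with at least one cycle and one scan, who withdraws consent fully at month 9.

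| Section | Status of this patient |
|---|---|
| 5.9, second case | Not evaluable for efficacy |
| 7.1.1 | Evaluable for response |
| 11.4, ORR | Included, as each patient is |
| 11.4, PFS and OS | Included; event if observed, otherwise censored |

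No section gives an order of precedence.

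**2. Random withdrawal, OS.** Assumptions: exponential survival with median 3.8 months (the Child-Pugh B figure for first-line sorafenib in Section 1.2, used only as an example) and constant withdrawal hazard μ.

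- Death hazard λ = ln 2 / 3.8 = 0.182 per month.
- Fraction withdrawn before death = μ / (λ + μ).
- Among those who do not withdraw, survival is exponential with hazard λ + μ, so the median is ln 2 / (λ + μ) and the 75th percentile is ln 4 / (λ + μ).

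| μ per month | Withdrawn | Median, excluded | 75th percentile, excluded |
|---|---|---|---|
| 0 | 0% | 3.8 | 7.6 |
| 0.02 | 0.02/0.202 = 9.9% | 0.693/0.202 = 3.4 | 1.386/0.202 = 6.8 |
| 0.04 | 0.04/0.222 = 18.0% | 0.693/0.222 = 3.1 | 1.386/0.222 = 6.2 |

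Censoring at withdrawal recovers 3.8 and 7.6, because withdrawal is unrelated to prognosis here.

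**3. Withdrawal at progression, PFS.** Assumptions: exponential PFS, again with median 3.8 months; withdrawal at progression with probability 2f if progression comes by 2.2 months and f/2 later. The proportion progressing by 2.2 months is 1 − exp(−0.182 × 2.2) = 0.331.

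- f = 0.1: withdrawn = 0.2 × 0.331 + 0.05 × 0.669 = 10.0%. The median m of the rest solves 0.95 exp(−λm) / 0.900 = 0.5, giving m = 4.1 months.
- f = 0.2: withdrawn = 0.4 × 0.331 + 0.1 × 0.669 = 19.9%. Then 0.90 exp(−λm) / 0.801 = 0.5, giving m = 4.4 months.

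The bias now goes upwards. Its direction and size follow from the assumed pattern.

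**4. ORR.** Assume three treated withdrawers, all replaced, and three responders among the other 32 patients. Intervals are exact 95%.

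| Case | All treated | Withdrawers excluded |
|---|---|---|
| One withdrawer had responded | 4/35 = 11.4% (3.2 to 26.7) | 3/32 = 9.4% (2.0 to 25.0) |
| No withdrawer had responded | 3/35 = 8.6% (1.8 to 23.1) | 3/32 = 9.4% (2.0 to 25.0) |

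The shift is about 1 to 2 percentage points, in either direction.

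**5. Sampling error for comparison.** With 32 events and an exponential model, the 95% interval for a 3.8-month median is 3.8 × exp(±1.96/√32), or 2.7 to 5.4 months. The shifts of 0.3 to 0.7 months above lie inside it.

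**6. The count.** Let w treated patients later meet 5.8.1 or 5.8.2.

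| Reading | Treated, all in TITE-CRM | Efficacy-evaluable under 5.9 | For w = 3 |
|---|---|---|---|
| Every dosed patient counts towards the 32nd | 32 | 32 − w | 32 and 29 |
| Withdrawers replaced to reach the total | 32 + w | 32 | 35 and 32 |

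A rough TITE-CRM simulation compared 32 with 35 patients. It used a one-parameter power model, skeleton 0.20/0.27/0.35, threshold 0.35, about one patient per 29 days, 500 runs, and prior SD 0.5, 0.8 or 1.34. Selection and early-stopping probabilities moved by at most about 4 points. One such change was 47% to 43%; the standard error of that difference, treating the runs as independent, is √(0.47×0.53/500 + 0.43×0.57/500) = 3.1 points. The simulation does not reproduce Table 7 (at SD 0.5, correct selection 47%/47%/73% against 70%/40%/90% stated), so it indicates scale only.

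**The case against.** The strongest reply is that 5.9 has a narrower purpose. After its first sentence, the second case is about patients who stop inside the DLT window, and the replacement sentence refers back to this type of patient. Replacement can fairly be read as confined to that window. That stands for replacement, but the efficacy exclusion carries no window on either reading.

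A reader might infer that the plan orders observed responses, progressions and survival times to be deleted. The documents do not say so: 5.9 calls the patients non-evaluable, and 7.1.1 and 11.4 would keep them. What exists is an unresolved conflict over the efficacy set.

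A reader might also infer that anyone who stops treatment is caught. That is not so: voluntary withdrawal from treatment is a separate criterion in 5.5, and 5.6 keeps such patients in follow-up. Only full withdrawal of consent, or loss of the ability to give it, triggers the rule.

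Nor do 5.9 and 11.4 state two different values of 32; 5.9 states no number. The ambiguity is whether replaced patients count. DLT data are expressly retained, so no primary-endpoint information is lost.

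Finally, the magnitudes rest on assumed withdrawal rates and concern descriptive secondary endpoints without a hypothesis test. That is correct and limits the weight of the point, but the bias is systematic and avoidable by wording.

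**Conclusion.** The point holds as a conflict between sections with a modest statistical consequence. Read literally, 5.9 removes treated patients from efficacy because of a post-treatment event, without a time limit; 7.1.1 and 11.4 keep them. If 5.9 were followed, the secondary estimates could be biased in either direction. Under the exponential assumptions, 10% to 18% random withdrawal lowers a 3.8-month median to 3.4 to 3.1, while 10% to 20% withdrawal concentrated at early progression raises it to 4.1 to 4.4. These rates are assumptions, and the effect is probably smaller than sampling error at 32 patients.

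The trigger in 11.4 is undefined by exactly w patients: 32 or 32 + w treated. The likely effect on dose selection is small. The documents do not support a claim that the RP2D is materially compromised.

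**What to change.** - **Section 5.9, efficacy.** Remove the non-evaluable status for treated patients. Keep all of them in PFS, TTP and OS, using events observed before withdrawal and otherwise censoring at the last assessment before it. Censoring assumes that withdrawal is unrelated to prognosis, so report the number and timing of withdrawals.
- **ORR.** Keep responses observed before withdrawal. State in advance whether the denominator is all treated patients or the 7.1.1 set.
- **Replacement.** Limit it to never-treated patients and to those who leave under 5.8.1 or 5.8.2 inside the DLT window without a DLT.
- **Sections 5.9, 7.1.1 and 11.4, count.** Say in all three whether replaced patients count towards the 32nd evaluable patient. Use all treated patients' DLT data, including partial data, in the final TITE-CRM estimate.

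The cost is wording; no new data are needed. Total treated may exceed 32 by the number of in-window withdrawals, which 5.9 already allows.
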